11.9.2 Clinical Data Management

All software applications used in the collection of data will be properly validated following standard computer system validation that is compliant with all regulatory requirements. All data, both eCRF and external data (e.g., laboratory data), will be entered into a clinical system.

12 STATISTICAL METHODS

12.1 General Statistical Considerations

Tabulations of summary statistics, graphical presentations, and statistical analyses will be performed using SAS® software. Descriptive statistics will be used to summarize data from this study, including mean, standard deviation, median, minimum, and maximum for continuous variables and frequency distributions and percentages for categorical variables. The specifics for these outputs will be described in detail within the Statistical Analysis Plan (SAP), which will be finalized before database lock.

The last observation prior to the first dose of study medication will be used as the baseline value for calculating post-administration changes from baseline. All data obtained on the eCRF will be presented in by-subject data listings.

Confidence intervals will be at the 95% confidence level unless stated otherwise.

Statistical analyses will be performed using SAS® software or other validated statistical software as required. Details of the statistical analyses will be included in a separate statistical analysis plan (SAP), which will be finalized before the database lock.

12.1.1 *Rationale for Sample Size*

The sample size of 20 subjects is considered adequate on clinical grounds to judge the safety of the combination therapy and obtain an initial estimate of its clinical efficacy.

The primary efficacy endpoint will be the overall response rate (ORR). The ORR for the combination therapy is hypothesized to exceed the value observed with ipilimumab monotherapy (10–15%, [Long et al., 2017](#)). A decision to officially expand enrollment beyond the planned approximately 20 subjects will depend on the number of responders in the first 20 evaluable subjects and will require a protocol amendment. To be considered evaluable, subjects must meet criteria for the Efficacy Evaluable population, be evaluable for tumor response as per RECIST v1.1 at 9 weeks, and have no major protocol deviations.

Evaluability for tumor response will be based on the following:

- Subjects who remain on study until the first evaluation (at 9 weeks) and have a tumor assessment performed.
- Subjects who withdraw from the study due to disease progression before the first evaluation (at 9 weeks) will be considered as subjects with early progression
- Subjects who die from malignant disease before the first evaluation (at 9 weeks) will be considered as subjects with early death

- Subjects with measurable disease, for whom all baseline target lesions have been assessed at least once after 9 weeks, with the same method of measurement used at baseline.
- Subjects with only non-measurable disease, for whom non-target lesions have been assessed at least once after 9 weeks.

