Pharmacokinetic (PK) Analysis Set: All subjects who receive at least one dose of FLX475 in combination with ipilimumab, and have measurable plasma concentrations of FLX475.

Pharmacodynamic (PD) Analysis Set: All subjects who receive at least one dose of investigational product and have sufficient PD data to derive at least one PD measurement.

Analysis Methods

Evaluation of data will consist primarily of descriptive statistics, summary displays, and data listings. Efficacy and safety data will be presented by treatment and tumor type. The number of subjects enrolled and discontinued from the study (by reason) will be presented. Demographic and baseline characteristics will be summarized for both the Safety Analysis Set and Efficacy Evaluable Set.

The incidence of adverse events will be presented by system organ class, preferred term, and maximum toxicity grade for subjects. Separate summaries will be provided for all adverse events, drug-related adverse events, serious adverse events, and adverse events leading to discontinuation of study treatment. Hematology and clinical chemistry data will be summarized by worst-case toxicity grade shift relative to baseline. Deaths will be listed by primary cause and date relative to last dose of study medication.

Efficacy endpoints will be summarized using descriptive statistics, including mean, standard deviation, median, and range for continuous endpoints and frequency tables for categorical data. Estimates of ORR and other response proportions will be presented together with 95%

confidence intervals calculated using the Clopper-Pearson method. Kaplan-Meier estimation will be used for the analysis of time-to-event endpoints, including DOR, PFS, and OS.

Rationale for Sample Size

The sample size of 20 subjects is considered adequate on clinical grounds to judge the safety of the combination therapy and obtain an initial estimate of its clinical efficacy. The ORR for the combination therapy is hypothesized to exceed the value observed with ipilimumab monotherapy (10–15%, [Long et al., 2017](#)).

To be considered evaluable, subjects must meet criteria for the Efficacy Evaluable Set (defined above), be evaluable as per RECIST v1.1 at 9 weeks, and should have no major protocol deviations. Evaluability for tumor response will be based on the following:

- Subjects who remain on study until the first evaluation (at 9 weeks) and are evaluated.

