6.3 Study Rationale

This Phase 2 study will evaluate safety and clinical efficacy, in addition to PK and potential changes in the TME of FLX475 in combination with ipilimumab in subjects with advanced melanoma. Ipilimumab is an approved treatment for advanced melanoma with a reported best overall response rate (ORR) ranging from 10.9% in previously-treated patients ([Hodi, et al., 2010](#)) to 19% in previously untreated patients ([Larkin, et al., 2015](#)), thus there remains room for clinical improvement.

The primary hypothesis of this study is that FLX475 administration may block the CCR4-mediated recruitment of T_{reg} into tumors, thus increasing the intratumoral $T_{eff}:T_{reg}$ ratio and favoring an anti-tumor immune response when given in combination with ipilimumab, thus increasing the clinical activity of ipilimumab. The study design will first examine the safety of the combination of FLX475 and ipilimumab as part of a safety run-in phase, and will also examine the degree of anti-tumor activity (clinical responses) in subjects with advanced melanoma previously treated with an anti-PD-1 or anti-PD-L1 agent. Based upon available clinical data, the ORR of ipilimumab monotherapy in such subjects is expected to be approximately 14% (Long, et al., 2017). Thus an ORR of >20–30% with the combination of FLX475 and ipilimumab in this study would provide preliminary clinical evidence in support of the clinical hypothesis.

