Subjects who, in the investigator's judgment, require the use of any of the aforementioned treatments for clinical management should be removed from the study. If a subject receives additional anticancer therapies, this will be judged to represent evidence of PD, and study treatment will be discontinued. These subjects should complete all End-of-Treatment assessments and continue to be followed for survival in the Follow-up Phase unless they withdraw consent or are lost to follow-up.

All treatments that the investigator considers necessary for a subject's welfare may be administered at the discretion of the investigator in keeping with the community standards of medical care.

All concomitant medication will be recorded on the eCRF, including all prescription, over-the-counter products, herbal supplements, and IV medications and fluids. If changes occur during the study period, documentation of drug dosage, frequency, route, and date should also be included on the eCRF.

Concomitant medications administered up to 90 days after the final dose of study treatment (or 30 days following cessation of study treatment if the subject initiates new anticancer therapy, whichever occurs first) should be recorded for SAEs and events of clinical interest (ECIs) as defined in [Section 11.5.2](#).

10.10.5 *Rescue Medication and Supportive Care*

Subjects should receive appropriate supportive care measures for an AE as deemed necessary by the treating investigator. Suggested supportive care measures for the management of AEs with potential immunologic etiology are outlined along with the dose modification guidelines in [Section 10.5.2](#). Where appropriate, these guidelines include the use of oral or IV treatment with corticosteroids, as well as additional anti-inflammatory agents if symptoms do not improve with administration of corticosteroids. Several courses of steroid tapering may be necessary, as symptoms may worsen when the steroid dose is decreased. For each disorder, an attempt should be made to rule out other causes, such as metastatic disease or bacterial or viral infection, which might require additional supportive care. The treatment guidelines are intended to be applied when the investigator determines the events to be related to ipilimumab (or FLX475). It may be necessary to perform conditional procedures such as bronchoscopy, endoscopy, or skin photography as part of the evaluation of the event.

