7.3 Study Subjects

7.3.1 *Disposition of Subjects*

Subject disposition will be summarized for all enrolled subjects by treatment group. Summaries will include the number and percentage of subjects in each analysis population, completing the treatment, discontinuing from treatment (by reason), completing the study, and discontinued from study (by reason).

7.3.2 *Protocol Deviations*

Protocol deviations (PDs) will be identified, logged, and reviewed during the course of the study. A determination of major versus minor PDs will be made according to the criteria outlined in the study protocol deviation review plan. A listing of all PDs will be provided. For purposes of CSR reporting, all important/major protocol deviations will be identified based on the following minimum criteria:

- Subjects who entered the study even though they did not satisfy the entry criteria.
- Subjects who developed withdrawal criteria during the study but were not withdrawn.
- Subjects who received the wrong treatment or incorrect dose.
- Subjects who received an excluded concomitant treatment.

7.3.3 *Demographic and Other Baseline Characteristics*

Demographic and baseline characteristics will be summarized descriptively for the Safety Analysis Set by treatment group. Gender, race, ethnicity, and baseline Eastern Cooperative Oncology Group (ECOG) performance status (PS) will be summarized with number and percentage presented for each category. Age, height, weight, and body mass index (BMI) at baseline will be described with summary statistics (n, mean, Std Dev, median, Q1, Q3, minimum, and maximum). BMI will be calculated as: weight (kg) / [height (cm) / 100]². In addition, primary cancer history will be summarized descriptively.

All demographic and baseline characteristics will be presented in a data listing.

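### The expansion count in Protocol 12.1.1 drops subjects with post-dosing major deviations, so it can lose treatment failures that the protocol itself judges to be progression

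*Protocol*

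**What the plan says.** Protocol 12.1.1 says that a decision to enroll beyond about 20 subjects "will depend on the number of responders in the first 20 evaluable subjects" and needs a protocol amendment. It gives no responder threshold. An evaluable subject must belong to the Efficacy Evaluable population and must also "be evaluable for tumor response as per RECIST v1.1 at 9 weeks, and have no major protocol deviations". The synopsis repeats the condition ("be evaluable as per RECIST v1.1 at 9 weeks, and should have no major protocol deviations") without mentioning expansion. Neither place limits the condition to deviations present before dosing. The bullets that follow in 12.1.1 name subjects who withdraw early for progression or die early of their cancer, and class them as early progression and early death.

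The protocol does not define a major deviation. SAP 7.3.2 gives minimum criteria for the study report, one of which is "Subjects who received an excluded concomitant treatment". It leaves the sorting of major from minor deviations to a separate deviation review plan.

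Protocol 10.10.4 prohibits other antineoplastic therapy, non-protocol immunotherapy and radiation during Screening and the Treatment Phase. Radiation to a single symptomatic lesion outside the target set, or to the brain, may be allowed. The same section states: "If a subject receives additional anticancer therapies, this will be judged to represent evidence of PD".

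**The concern.** Two rules treat the same event differently. Under 10.10.4, starting another anticancer therapy on study is progression. Under 12.1.1 read with SAP 7.3.2, it is a reason to leave the group on which the expansion decision rests. Because the rule takes the first 20 evaluable subjects, the next one fills the vacancy, and the denominator of 20 does not show the loss. This can happen even to a subject who has a week-9 scan and belongs to the Efficacy Evaluable Set.

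The exclusion is made after baseline and can depend on outcome. The bullets on early progression and early cancer death suggest that failures were meant to count, and the deviation clause works against that. At stake is a decision to enlarge the trial on a responder count that looks better than the result in treated subjects, set against an ipilimumab-alone rate "expected to be approximately 14"% (Protocol 6.3).

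**Working it through.** **The plan's own figure.** Protocol 12.1.1 states: "The sample size of 20 subjects is considered adequate on clinical grounds". With no alpha, power, formula or threshold, there is nothing to reproduce. What follows illustrates the possible size of the effect.

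**Inputs from the documents.**
- Ipilimumab-alone ORR: about 14% (Protocol 6.3), or 10–15% (12.1.1).
- ORR of interest: above 20–30% (6.3), a gain of 6 to 16 points over 14%.
- Decision set: 20 subjects (12.1.1).

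**Assumptions, not in the documents.**
- *d*, the share of otherwise countable subjects excluded for post-dosing deviations: 5% to 20%.
- *r*, the response rate among those excluded: 0 in the main case.
- A cut-off of 5 responders in 20.

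**Formula.** With ORR *p* before the exclusion, the ORR among those who stay in the count is

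p_eval = (p − d·r) / (1 − d)

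The chance of reaching the cut-off is the binomial tail P(X ≥ 5) with n = 20 and probability p_eval.

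**Main case, p = 14%, r = 0.**

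| d | p_eval | P(≥5 of 20) |
|---|---|---|
| 0 | 14.0% | 13.7% |
| 5% | 0.14/0.95 = 14.7% | 16.1% |
| 10% | 0.14/0.90 = 15.6% | 19.0% |
| 20% | 0.14/0.80 = 17.5% | 26.4% |

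At d = 10% the shift is 15.6 − 14.0 = 1.6 points. That is about 10% of a 16-point gain (1.6/16) and about 26% of a 6-point gain (1.556/6, using the unrounded shift). At d = 20% the chance of reaching the cut-off with an inactive add-on nearly doubles.

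**Range over the stated benchmark.** At p = 10%, P(≥5) goes from 4.3% to 9.5% at d = 20%. At p = 15%, it goes from 17.0% to 31.6%.

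**Sensitivity to r.** The bias is zero when r = p and reverses when r > p. With p = 14% and d = 10%:
- r = 5%: (0.14 − 0.005)/0.90 = 15.0%, still upward.
- r = 20%: (0.14 − 0.02)/0.90 = 13.3%, downward.

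**On observed counts.** With 5 responders in 20 (25.0%), adding back 1, 2 or 4 excluded non-responders gives 5/21 = 23.8%, 5/22 = 22.7% or 5/24 = 20.8%. The Clopper-Pearson 95% interval for 5/20 is 8.7% to 49.1%.

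**Which analyses carry the condition.** Protocol 12.1.6 analyzes tumor endpoints in the FAS and the Efficacy Evaluable Set, with the Efficacy Eligible Set as a sensitivity analysis of ORR. None of the three definitions in 12.1.2.3 mentions deviations. Only the evaluability rule in 12.1.1 and the synopsis, and the optional Per-Protocol population, do.

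**The case against.** The case on the other side is substantial, and several parts of it stand.

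- **The trial's ORR.** A reader might infer that these subjects leave the ORR denominator in general. They do not: the sets planned for ORR have no deviation condition. The point concerns the expansion count only.
- **Radiotherapy.** A reader might infer that any palliative radiotherapy removes a subject. Radiation allowed under the exception in 10.10.4 is not an excluded treatment. The sentence equating therapy with progression also does not name radiotherapy, so the conflict is clearest for systemic anticancer therapy.
- **Ordinary failures.** A reader might infer that everyone who moves on to another treatment is dropped. The prohibition covers only Screening and the Treatment Phase, and the Table 6 footnote places the end-of-treatment assessments before any other treatment. A subject who progresses, stops, completes that visit and then starts new therapy has not deviated. Subjects with no post-baseline tumor assessment already fail the Efficacy Evaluable definition, so the clause adds nothing for them.
- **The link to the SAP.** Reading the protocol's term through SAP 7.3.2 is an inference. The list serves the study report, defers to a plan outside these documents, and stands in a SAP that was written after the study stopped and has no expansion rule. This stands, but it also means that a condition on the expansion decision is undefined in the protocol.
- **Size and direction.** No document gives a deviation rate, and the other SAP criteria, such as a wrong dose or unmet entry criteria, have no evident direction. The shifts shown are small beside the width of the interval for 5/20.

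None of this removes the narrower conflict. Followed as written, the rule can take out a subject whom 10.10.4 judges to have progressed and replace that subject with another.

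**Conclusion.** The point holds for the expansion count alone. Protocol 12.1.1 makes that count conditional on an event that can arise after dosing. If major deviations are read as in SAP 7.3.2, taking prohibited anticancer therapy, or radiotherapy outside the exception, during the Treatment Phase removes the subject.

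The likely direction is upward for anticancer therapy, because 10.10.4 equates it with progression, but no document gives a frequency. At a true ORR of 14%, the upward direction needs excluded subjects to respond less often than 14%. If all of them are non-responders, excluding 5% to 20% raises the expected ORR in the count to between 14.7% and 17.5%. The exclusion rates and the cut-off of 5 are illustrative assumptions, not features of the plan.

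Urgency is low. The study was discontinued early, SAP 7.4.1 and 7.7 say that efficacy will not be summarized, and any expansion would have needed an amendment. The correction matters mainly if the design or its wording is used again.

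**What to change.** Change Protocol 12.1.1 and the matching synopsis sentence. The SAP has no expansion text to change.

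1. Limit the deviation exclusion to eligibility failures identified from pre-dose data without knowledge of response.
2. State that a subject who starts prohibited anticancer therapy before a confirmed response counts as a non-responder in the expansion count, in line with 10.10.4.
3. Keep the deviation-free subset only as the optional Per-Protocol analysis already in 12.1.2.3.

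The cost is a few sentences, with no new data or subjects. The ORR used for the decision becomes slightly lower where such subjects occur. The change does not touch the separate Efficacy Evaluable requirement of one completed cycle and a post-baseline assessment, which is also a post-baseline filter on the same count.

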12.1.2 Statistical and Analytical Plans

The statistical analyses of the primary analysis of the study data are described in this section. Further details of the analytical plan will be provided in the SAP, which will be finalized before database lock.

Based on the FAS, information regarding study treatment administration, study treatment compliance, safety variables, and poststudy therapies will be described and summarized.

12.1.2.1 Study Endpoints

12.1.2.1.1 Safety Endpoints

The primary safety endpoint of the study is safety and tolerability by the determination of AEs, including DLTs. The following safety parameters will be characterized and summarized:

- Treatment-emergent adverse events (TEAEs) and SAEs together with all other safety parameters
- Number (%) of subjects who discontinue treatment due to TEAEs
- Time to treatment failure due to toxicity, defined as the time from the date of start of treatment to the date that a subject discontinues study treatment due to TEAEs
- Dose-limiting toxicity (defined in [Section 10.4](#))
- Laboratory abnormalities
- Vital sign abnormalities
- Adverse ECG findings

12.1.2.1.2 Efficacy Endpoints

The primary efficacy endpoint of the study is objective response rate (ORR), defined as the proportion of subjects who have best overall response of CR or PR as determined using RECIST 1.1 ([Appendix 4](#)).

Other efficacy endpoints are as follows:

- Overall Survival (OS), defined as the time from the date of start of treatment to the date of death from any cause. Subjects who are lost to follow-up and those who are alive at the date of data cutoff will be censored at the date the subject was last known alive, or date of data cutoff, whichever occurs first.
- Clinical Benefit Rate (CBR), defined as the proportion of subjects who achieve a CR, a PR, or durable SD duration of at least 6 months from start of study treatment)
- Time to Response, defined as the interval from start of study treatment to the first documentation of CR or PR
- Duration of Response, defined as the interval from the first documentation of CR or PR to the earlier of the first documentation of PD or death from any cause
- Progression-free Survival (PFS), defined as the interval from the start of study treatment to the earlier of the first documentation of PD or death from any cause

12.1.2.2 Pharmacokinetic and Pharmacodynamic Endpoints

Plasma concentrations of FLX475 will be listed and summarized by time point. No PK parameters (e.g. C_{max} and AUC) will be calculated.

Pharmacodynamic endpoints are as follows:

- Changes in immune parameters, e.g., lymphocyte subpopulations and plasma cytokines or chemokines in peripheral blood or in tumor

Using data from the relevant evaluable data sets, study treatment plasma concentrations and PD markers will also be described and summarized.

12.1.2.3 Analysis Sets

The allocation of subjects to analysis sets will be determined prior to database lock. For the purpose of analysis, the following populations will be defined:

Full Analysis Set: All subjects enrolled in the study, also known as the “Intent-to-Treat” (ITT) population.

Safety Analysis Set: All subjects who receive at least one dose of the investigational product, FLX475 (even a partial dose).

Efficacy Eligible Set: All subjects who receive at least one dose of FLX475 in combination with ipilimumab, have measurable disease at baseline per RECIST v1.1, and have at least

one post-baseline scan or discontinue study treatment as a result of progressive disease, death, or a treatment-related adverse event before the first post-baseline scan.

Efficacy Evaluable Set: All subjects who complete at least one cycle of FLX475 and ipilimumab and have a baseline and at least one post baseline on-study assessment of tumor response.

As warranted by the data, efficacy may also be assessed in a Per-Protocol Population comprising all Efficacy Evaluable subjects who have no major protocol violations, as defined by the Sponsor prior to database lock.

Pharmacokinetic (PK) Analysis Set: All subjects who receive at least 1 dose of FLX475 in combination with ipilimumab and have measurable plasma concentrations of FLX475.

Pharmacodynamic (PD) Analysis Set: All subjects who receive at least 1 dose of investigational product and have sufficient PD data to derive at least 1 PD measurement.

12.1.3 *Subject Disposition*

The number and percentage of subjects who are enrolled, treated, complete the study, and discontinue from the study will be presented for the Full Analysis Set. A summary of reasons for discontinuation will be provided. The number of subjects included in the Safety Analysis and Efficacy Evaluable Sets will be summarized and the reasons for excluding subjects from the Efficacy Analysis Set will be listed.

12.1.4 *Demographic and Other Baseline Characteristics*

Descriptive statistics will be used to summarize demographic and baseline characteristics of subjects in each analysis set. Subject characteristics to be tabulated include: age, sex, race, ethnicity, baseline performance status, primary diagnosis, disease stage at diagnosis and baseline, prior therapies (including systemic therapies, radiation, and surgeries), and best response to prior cancer therapies.

12.1.5 *Prior and Concomitant Therapy*

All investigator terms for medications recorded in the eCRF will be coded to an 11-digit code using the World Health Organization Drug Dictionary (WHO DD) drug codes. The number (percentage) of subjects who took prior and concomitant medications will be summarized for the FAS by treatment, Anatomical Therapeutic Chemical class, and WHO DD preferred term. Prior medications will be defined as medications that were stopped before the first dose of study treatment. Concomitant medications will be defined as medications that (1) started before the first dose of study treatment and were continuing at the time of the first dose of study treatment, or (2) started on or after the date of the first dose of study treatment up to 30 days after the subject's final dose. All medications will be presented in subject data listings.

12.1.6 *Efficacy Analyses*

The primary efficacy endpoint is ORR, and the secondary efficacy endpoints include PFS, TTR, DOR and OS. Tumor-related endpoints will be analyzed for the FAS and Efficacy Evaluable Sets, as appropriate. An additional sensitivity analysis of ORR will be performed for the Efficacy Eligible Set. Efficacy will also be explored in subgroups of special interest, notably subjects who are anti-PD-(L)1 refractory (as defined in [Appendix 8](#)) and other prognostic subgroups pre-specified in the SAP.

ORR will be defined as the proportion of subjects who are responders, i.e., CR and PR; the exact 95% confidence interval for ORR will be calculated using the Clopper-Pearson method. The CBR (CR + PR + SD) will also be calculated; SD in the CBR determination is defined as SD that persists for ≥ 6 months. The ORR and CBR analysis will be based on RECIST v1.1.

Time-to-event endpoints, including PFS and OS, will be summarized descriptively and graphically using Kaplan-Meier (KM) methodology. KM estimates for the median, first, and third quartiles will be determined along with 95% confidence intervals (CIs). The Brookmeyer-Crowley method will be used for the CI calculations. For the subset of subjects who have a CR or PR, DOR will be summarized similarly using the Kaplan-Meier method. TTR will be defined from the start of treatment to the first documented CR or PR and will be summarized descriptively as a continuous variable.

PFS is defined as the time from the date of initiation of FLX475 to the date measurement criteria are first met for irPD/PD or death from any cause, whichever occurs first. For subjects still alive at the time of analysis and without evidence of irPD/PD, PFS will be censored on the date of the most recent objective progression-free observation. For subjects who receive subsequent anticancer therapy prior to irPD/PD or death, PFS will be censored on the date of the last objective progression-free observation prior to the date of subsequent therapy.

DOR is defined as the time from first date measurement criteria are met for irPR/PR or irCR/CR (whichever status is recorded first) to the date measurement criteria are first met for irPD/PD or the date of death, whichever is sooner. For subjects not known to have died as of the data cut-off date and who do not have irPD/PD, DOR will be censored at the last progression-free assessment date. For responding subjects who receive subsequent anticancer therapy (after discontinuation from all study treatment) prior to disease progression, DOR will be censored at the date of last progression-free assessment prior to the initiation of a new anticancer therapy.

OS is defined as the time from the date of initiation of FLX475 to the date of death from any cause. For subjects who are still alive as of the data cut-off date, OS time will be censored on the date of the subject's last contact (last contact for subjects post-treatment = last known alive date in mortality status).

12.1.7 *Pharmacokinetic, Pharmacodynamic, Pharmacogenomic, and Other Biomarker Analyses*

